### **8.2 Statistical Analysis Plan**

8.2.1 As a phase 1b study, the analysis of results will be descriptive in nature. This study will estimate:

- ORR at days 35 and 77 in subjects receiving pembrolizumab monotherapy
- ORR at day 77 in subjects receiving pembrolizumab  $\pm$  standard induction chemotherapy
- Clinical Benefit Rate (CBR) at days 35 and 77 in subjects receiving pembrolizumab monotherapy

Safety:

- Incidence and severity of GvHD after administration of pembrolizumab to include analysis of:
  - a) incidence of severe acute GvHD events (grade 3-4) during induction treatment and within 30 days of last pembrolizumab infusion during induction treatment (as described in sections 7.2 and 8.1).
  - b) incidence of total GvHD events (acute GVHD grade 2-4, new onset chronic GVHD) that occur in subjects during treatment (both induction and maintenance) and in follow up through 90 days after last pembrolizumab infusion. Subjects taken "off-study" will be censored if they receive other immune therapies (e.g. DLI).

- Grade 3-5 Regimen-related toxicities (RRT) per CTCAE v4
- Incidence of immune mediated toxicities attributable to pembrolizumab

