Correlative Studies: Blood Collection§, ¶		X	D14 (+5)	D35 (±5)	D56 (±5)		X	D168 (±7) D252 (±7)		X	D425 (±14)†	X
Correlative Studies: Buccal Swabs		X										
Chimerism Analysis (VNTR) (Peripheral Blood)**		X		X			X			X		X

\*Phase II Maintenance treatment: For subjects achieving CR / PR as determined by day 77 response post-induction without significant pembrolizumab related toxicity. Subjects without CR / PR at day 77, relapse / progression after day 77 or clinically significant toxicity during the treatment will be considered off treatment and will be placed into follow-up.

†Follow up: Toxicity assessments will be for 30 days after last dose of pembrolizumab. Longer follow-up for up to 90 days, if applicable, based on continuing SAE / AE that was observed in the treatment period or an events of clinical interest (ECI). Follow up for survival will be up to 90 days after pembrolizumab or D455 (±14) for subjects completing

maintenance and a research blood collection will be obtained. Subjects not initiating or completing maintenance will complete 30 day toxicity assessments and then be followed only for survival (through D365 after initiating pembrolizumab). Subjects in CR/PR not completing maintenance for toxicity may have additional research specimens collected per investigators discretion (see below note). ‡ Relapse denotes collection of unplanned / unscheduled bone marrow aspirate, biopsy and correlative studies at time of clinical suspicion of relapse (if CR) or progression of malignancy at any time during treatment and follow-up periods.

§Bone marrow morphology based on aspirate and/or core biopsy, flow cytometry and  $\pm$  cytogenetics will be performed on day 35 (+5) after dose #2, day 77 ( $\pm$ 7) after dose #4, day 365 ( $\pm$ 14) after completing maintenance. An end of treatment bone marrow may be performed prior to day 365 in subjects in CR/PR who do not complete full maintenance therapy due to toxicity. Subjects removed from further treatment due to documented relapse are not required to undergo further bone marrow studies for research purposes. Cytogenetic analysis may be omitted if there are not pre-treatment cytogenetic anomalies of clinical interest.

||Comprehensive Serum Chemistry Panel should include Magnesium and Phosphorus.

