#### **7.1.1.5.3 Subsequent Anti-Cancer Therapy Status**

The investigator or qualified designee will review all new anti-neoplastic therapy initiated after the last dose of trial treatment. Once new anti-cancer therapy has been initiated the subject will move into survival follow-up.

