### **7.1.1.6 Assignment of Screening Number**

**A screening number will be assigned to all subjected being screened.**

## **7.1.2 Clinical Procedures/Assessments**

### **7.1.2.1 Adverse Event (AE) Monitoring**

The investigator or qualified designee will assess each subject to evaluate for potential new or worsening AEs as specified in the Trial Flow Chart and more frequently if clinically indicated. Adverse experiences will be graded and recorded throughout the study treatment and during the safety follow-up period (30 days after the last dose of pembrolizumab) according to NCI CTCAE Version 4.0 (see Section 11.3). Adverse events in the post-treatment follow up period will not be recorded or reported unless they represent continuing adverse events from the treatment period related to pembrolizumab therapy.

Toxicities will be characterized in terms regarding seriousness, causality, toxicity grading, and action taken with regard to trial treatment.

For subjects receiving treatment with pembrolizumab all AEs of unknown etiology associated with pembrolizumab exposure should be evaluated to determine if it is possibly an event of clinical interest (ECI) of a potentially immunologic etiology (termed immune-related adverse events, or irAEs); see the separate ECI guidance document in Appendix 4 regarding the identification, evaluation and management of potential irAEs.

Please refer to section 7.2 for detailed information regarding the assessment and recording of AEs.

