##### 7.1.4.3 Treatment Period

**"Treatment Period"** is defined as the first day of pembrolizumab through 30 days after the last dose of pembrolizumab – from 1st to 4th doses (or 17th dose if receiving maintenance). The assessment and reporting period for **adverse events (AE) related to the pembrolizumab** will start from the first pembrolizumab administration until 30 days after the last pembrolizumab administration.

**"Follow-up Period"** is defined as the first day the subject is no longer within the treatment period (e.g. 31 days after last administration of pembrolizumab) until six months after date of initiating study treatment.

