##### 7.1.4.4 Post-Treatment Visits

###### 7.1.4.4.1 Safety Follow-Up Visit

The mandatory Safety Follow-Up Visit should be conducted approximately 30 days after the last dose of trial treatment. All AEs that occur prior to the Safety Follow-Up Visit should be recorded. Subjects with an AE of Grade > 1 will be followed until the resolution of the AE to Grade 0-1 or until the beginning of a new anti-neoplastic therapy, whichever occurs first. SAEs that occur within 30 days of the end of treatment or before initiation of a new anti-cancer treatment should also be followed and recorded.

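### GvHD component (b) runs to 90 days after the last infusion, but the collection rules conflict on days 31 to 90, mainly for subjects who do not start or complete maintenance

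*Combined protocol and SAP*

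**What the plan says.** Section 4.2.2.1 lists the incidence and severity of GvHD among the primary safety endpoints. Section 8.2.1 splits this into (a), severe acute GvHD during induction and up to 30 days after the last induction infusion, and (b), grade 2-4 acute plus new-onset chronic GvHD over all treatment and "in follow up through 90 days after last pembrolizumab infusion". For (b), the only stated reason to censor an off-study subject is receipt of another immune therapy such as DLI.

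The collection sections set shorter limits:

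- Section 7.1.2.1: "Adverse events in the post-treatment follow up period will not be recorded or reported unless they represent continuing adverse events from the treatment period" and are related to pembrolizumab.
- Section 7.1.4.3: the assessment and reporting period for related adverse events "will start from the first pembrolizumab administration until 30 days after the last pembrolizumab administration". The Follow-up Period then begins and lasts "until six months after date of initiating study treatment".
- Section 7.1.4.4.1, on the visit about 30 days after the last dose: "All AEs that occur prior to the Safety Follow-Up Visit should be recorded".
- Section 6.0, follow-up footnote: "Toxicity assessments will be for 30 days after last dose of pembrolizumab", extended to 90 days only for a continuing event from the treatment period or an event of clinical interest (ECI). It adds: "Subjects not initiating or completing maintenance will complete 30 day toxicity assessments and then be followed only for survival".
- Section 7.1.1.5.3: "Once new anti-cancer therapy has been initiated the subject will move into survival follow-up".

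Other text points the other way. The flow chart marks adverse event review and a directed examination in a 30- and 90-day follow-up column. Section 5.6 gives 90 days for serious events and cites section 7.2.3.1, which gives 30. Section 7.2.3.1 also makes related serious events reportable at any time. Section 8.2.4 says that grade 2 GvHD is recorded.

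**The concern.** An incidence to day 90 needs every treated subject to be assessed for GvHD to day 90, or censored when assessment stops. The plan secures neither. A subject who leaves treatment and moves to survival-only follow-up is not assessed for GvHD after about day 30, yet nothing in (b) removes that subject from the risk set. Read as written, the subject counts as free of GvHD to day 90.

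Component (b) is the only planned GvHD analysis that names grade 2 acute and new-onset chronic GvHD. Section 8.2.4 frames the safety question as an increase over the expected baseline and gives that baseline as 40-50% for grade 2-4 acute GvHD. An undercount in (b) would make that comparison look more favourable than it is. The loss is also not random: section 7.1.4.5.1 sends subjects to survival follow-up because of treatment-related toxicity, lack of response after induction, or progression.

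**Working it through.** The plan attaches no figure to (b), so there is none to reproduce. The check sets the windows side by side and does calendar arithmetic.

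**Possible recording routes for a first GvHD event on days 31-90**

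1. General adverse event recording (7.1.2.1, 7.1.4.3): closed to new events after day 30.
2. Section 7.2: requires non-hematologic events of grade III or higher, through 30 days. Grade 2 GvHD is below that grade. Events are then recorded at each examination with no end date, but the GvHD forms given as examples are hyperacute and severe acute.
3. Serious events: 90 days in 5.6, 30 days in 7.2.3.1. Beyond that, only events judged related are reportable.
4. ECIs (7.2.3.2): 90 days, falling to 30 once new anticancer therapy starts. GvHD is not on the list in that section.
5. Section 8.2.4: grade 2 GvHD is recorded, but the monitoring window stated there is induction plus 30 days.
6. The 90-day visit: marked in the flow chart, but the footnote takes subjects who do not start or complete maintenance off it.

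No collection section names chronic GvHD.

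**Calendar.** On the three-week schedule, dose k falls on day 1 + 21(k - 1). General recording ends 30 days after the last infusion, and window (b) ends 90 days after it.

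| Last dose | Day | +30 | +90 |
|---|---|---|---|
| 2 | D22 | D52 | D112 |
| 4 | D64 | D94 | D154 |
| 5 | D85 | D115 | D175 |
| 6 | D106 | D136 | D196 |
| 14 | D274 | D304 | D364 |
| 15 | D295 | D325 | D385 |
| 16 | D316 | D346 | D406 |
| 17 | D337 | D367 | D427 |

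- The unclear period is days 31-90, which is 60 days for each subject.
- Six months from first dose is about D183. The Follow-up Period of 7.1.4.3 therefore contains the whole window if the last dose is dose 5 (D175) but not if it is dose 6 (D196) or later. Completers are affected by this definition too.
- The footnote ends survival follow-up of non-completers at D365. The window is inside that limit after dose 14 (D364) but outside it after dose 15 (D385) or dose 16 (D406).
- Section 7.1.4.5.1 sets contacts at least every 8 weeks, or by phone every 12 weeks. Counted from the day-30 visit (an assumption, since no starting point is stated), the next contact falls by day 30 + 56 = 86, inside the window, or as late as day 30 + 84 = 114, after it closes.

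**Illustration only.** Suppose a share s of subjects with an event have their first event on days 31-90 and all of these are missed. Observed incidence is then I(1 - s). The documents do not give s, so take 10% to 30% as an assumption. At the plan's 40% background, observed incidence would be 0.40 × 0.90 = 36% down to 0.40 × 0.70 = 28%. At 50%, it would be 45% down to 35%. The background figure covers acute GvHD only and carries no time window, so this shows direction and scale and is not an estimate.

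**The case against.** The strongest reply is that the restrictive reading is not the only one.

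- **90-day extension.** The footnote allows follow-up to 90 days for some events, and section 7.1.2.1 refers to separate ECI guidance that is not in the text and could cover GvHD. This stands as an uncertainty. As written, though, the extension covers only continuing events and ECIs, and the ECI window shortens once new anticancer therapy starts.
- **Other follow-up.** Sections 5.6 and 7.1.4.5 keep subjects who stop for reasons other than progression under follow-up for disease status, and survival contacts are coordinated with routine transplant visits. A subject who stops after dose 2 may also have the D77 visit, day 55 after the last infusion, with adverse event review marked. GvHD may well be seen at these contacts, but no rule requires a first occurrence to be recorded, and section 7.1.2.1 says it is not.
- **Section 7.2 list.** Its GvHD items are examples, so silence on chronic GvHD is weak evidence taken alone. That is fair. The case rests on the cut-off and the footnote.
- **New therapy and end of study.** Section 7.1.4.5.1 limits the move to survival follow-up to therapy outside the protocol, and its end-of-study wording is ambiguous for a last infusion at dose 15 or 16. Both points are right, and both leave text to be reconciled.
- **Bias is inferred.** Section 8.2.1 names no estimator and does not say that unassessed subjects count as event-free. True, but it states no censoring for them either, and unrecorded events can only reduce the count.
- **Consequence.** The analysis is descriptive in 20 subjects and no stated decision rule uses (b). This limits the severity without removing the defect.

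**Conclusion.** The concern holds. The window of (b) and the collection rules contradict each other for days 31-90, chiefly for subjects who do not start or complete maintenance and to a lesser degree for completers. Followed as written, the restrictive rules would miss first-onset, non-serious GvHD in that period and understate a component of a primary safety endpoint. The direction is downward. The size cannot be derived, because the documents give neither GvHD onset times nor the expected number of non-completers.

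Component (a), the section 8.1 estimate and the stopping rule all use 30-day windows and are untouched. The conclusion assumes that the unseen ECI guidance does not bring all GvHD into 90-day reporting. Even if it did, the shorter ECI window after new anticancer therapy would remain. This should be fixed, but it does not threaten the trial's stated decision rules.

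**What to change.** Make collection match the endpoint:

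- Exempt GvHD from the cut-off in section 7.1.2.1, and align the section 6.0 footnote and the Follow-up Period in section 7.1.4.3. Record GvHD type (acute or chronic), onset date and maximum grade for every treated subject through 90 days after the last infusion.
- Use the existing 30/90-day visit where it applies, and routine transplant follow-up records and planned survival contacts elsewhere. Add a GvHD item with onset date to the contact form, so that a phone contact after day 90 still recovers an event inside the window.
- Let GvHD collection run past D365 for non-completers whose last infusion is dose 15 or 16.
- In section 8.2.1(b), censor at the last GvHD assessment where 90-day information is missing, and report how many subjects have complete 90-day data.
- Reconcile the windows for serious events in sections 5.6 and 7.2.3.1.

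If collection is not extended, shorten (b) to 30 days and state that later GvHD was not assessed.

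The cost is protocol wording and slightly more data abstraction, with no added visit. The reported GvHD rate may be higher.

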## 6.0 TRIAL FLOW CHART

Study Period:	Screening Phase		Treatment Cycles Phase I: Induction				Response Post- Induction	Treatment Cycles Phase II: Maintenance	Response Post- Maintenance	Post-Treatment	
Treatment Dose/Title Day (D)	Pre- screening	Main Study Screening	1 (D1)	2 (D22)	3 (D43)	4 (D64)	(D77)	Doses 5 – 17 (D85 - D365)*	End of Treatment (D365)	Follow-up: 30 and 90 Days After Treatment up to D455†	Relapse‡
Scheduling Window (Days):	Days -21 to -1	Days -21 to -1	± 3	± 3	± 3	± 3	±7	± 3	± 14	± 14	n/a
Administrative Procedures											
Informed Consent		X									
Inclusion/Exclusion Criteria	X	X									
Subject Identification Card		X									
Demographics and Medical History		X									
Prior and Concomitant Medication Review		X					X				
Study Treatment Administration			X	X	X	X		X			
Post-study Therapy Response Status									X		
Survival Status									X		X
Clinical Procedures/Assessments											
Review Adverse Events		X	X	X	X	X	X	X	X	X	
Full Physical Examination		X	X	X	X	X	X				
Directed Physical Examination								X	X	X	
Vital Signs and Weight		X	X	X	X	X	X	X	X	X	
ECOG OR Karnofsky Performance Status		X	X	X	X	X	X	X			
Laboratory Procedures/Assessments: analysis performed by LOCAL laboratory											
Pregnancy Test – Urine or Serum b-HCG		X	X	X	X	X	X				
PT/INR and aPTT		X	X	X	X	X					
CBC with Differential		X	X	X	X	X	X	X	X	X	
Comprehensive Serum Chemistry Panel		X	X	X	X	X	X	X	X	X	
LDH and Uric acid		X	X	X	X	X					
Urinalysis		X	X	X	X	X		X			

Study Period:	Screening Phase		Treatment Cycles Phase I: Induction				Response Post- Induction	Treatment Cycles Phase II: Maintenance		Response Post- Maintenance	Post-Treatment	
Treatment Dose/Title Day (D)	Pre- screening	Main Study Screening	1 (D1)	2 (D22)	3 (D43)	4 (D64)	(D77)	Doses 5 – 17 (D85 - D365)*		End of Treatment (D365)	Follow-up: 30 and 90 Days After Treatment up to D455†	Relapse‡
Scheduling Window (Days):	Days -21 to -1	Days -21 to -1	± 3	± 3	± 3	± 3	±7	± 3		± 14	± 14	n/a
T3, FT4 and TSH		X	X	X	X	X		X				
Efficacy Measurements												
Bone Marrow Morphology§				D35 (±5)			X			X		X
Bone Marrow Flow Cytometry§				D35 (±5)			X			X		X
Bone Marrow Cytogenetics§				D35 (±5)			X			X		X
Tumor Biopsies/Archival Tissue Collection/Correlative Studies Blood												
Pre-transplant Bone Marrow Biopsy Specimen Collection		X										
Correlative Studies: Bone Marrow Aspirate§		X		D35 (±5)			X			X		X

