##### **7.1.4.5.1 Survival Follow-up**

If a subject experiences a treatment related adverse event that necessitates their removal from further study treatment, starts a new anti-cancer therapy (non-protocol defined therapy), does not achieve after induction (phase I), develops progression during maintenance (phase II) or completes planned treatment phase the subject moves from treatment into the survival follow-up phase and will be followed at a minimum of every 8 weeks to assess for survival status until death, withdrawal of consent, or the end of the study (1 year after initiation of pembrolizumab or 90 days after last maintenance dose of pembrolizumab), whichever occurs first (please reference section 5.2.1.2 of this protocol regarding permitted chemotherapies on-protocol). These visits will be coordinated with routine BMT follow-up. If follow-up is not feasible (e.g. patient leaves center) phone contacts will be made every 12 weeks.

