From the time of treatment allocation/randomization through 30 days following cessation of treatment, **all non-hematologic grade  $\geq$  III adverse events must be reported by the investigator. Investigators will monitor patients carefully for early evidence of transplant-related complications, such as hyperacute graft-versus-host disease (GVHD), severe acute GVHD, steroid-requiring febrile syndrome, hepatic veno-occlusive disease, and other immune-mediated adverse reactions.** Such events will be recorded at each examination on the Adverse Event case report forms/worksheets. The reporting timeframe for adverse events meeting any serious criteria is described in section 7.2.3.1. The investigator will make every attempt to follow all subjects with non-serious adverse events for outcome.

Adverse events will not be collected for subjects during the pre-screening period (for determination of archival tissue status) as long as that subject has not undergone any protocol-specified procedure or intervention. If the subject requires a blood draw, fresh tumor biopsy etc., the subject is first required to provide consent to the main study and AEs will be captured according to guidelines for standard AE reporting.

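### Adverse event recording is tied to the last pembrolizumab dose, so for subjects switched early to protocol chemotherapy it can end about 25 days before the day 77 response assessment

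*Combined protocol and SAP*

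**What the plan says.** Objective 1 (3.1.1) is the safety of pembrolizumab with or without chemotherapy. Among the primary endpoints in 4.2.2.1, repeated in 8.2.1, are the day 77 response rate with or without induction chemotherapy and "Grade 3-5 Regimen-related toxicities (RRT) per CTCAE v4". The RRT line has no window, no definition of the regimen and no attribution rule. Its neighbours do have windows: 8.1 and 8.2.1 give them for severe acute GvHD, total GvHD and immune-mediated toxicity of grade 3 or more.

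Under 5.2, a subject who starts induction chemotherapy for progression gets no further induction pembrolizumab. Maintenance is possible, but not assured, if day 77 shows PR or CR.

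The recording rules are anchored to pembrolizumab:

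- 7.1.4.3: the treatment period "is defined as the first day of pembrolizumab through 30 days after the last dose of pembrolizumab". Section 8.1 uses the same end point.
- 7.1.2.1: events after that "will not be recorded or reported unless they represent continuing adverse events from the treatment period related to pembrolizumab therapy".
- 6.0, follow-up footnote: "Subjects not initiating or completing maintenance will complete 30 day toxicity assessments and then be followed only for survival".

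Other text sits uneasily with this. The "Review Adverse Events" row of the flow chart is marked at D77, with no exception for switched subjects. Section 7.2 requires reporting of non-hematologic events of grade III or above "From the time of treatment allocation/randomization through 30 days following cessation of treatment", without naming the treatment. For SAEs, 5.6 states 90 days after the end of treatment and cites 7.2.3.1, which says 30 days.

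**The concern.** Efficacy and safety of the same sequence are measured over different periods. A switched subject can count as a responder to pembrolizumab plus chemotherapy at D77, while new toxicity in the preceding weeks falls outside the recording rule. The permitted regimens include high-dose cytarabine and anthracycline combinations (5.2.1.2), and 5.2 itself raises possible synergy between pembrolizumab and chemotherapy. Section 5.2.1.2 adds that pembrolizumab events may appear several weeks after the last dose.

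At stake is the reported grade 3-5 RRT rate, a primary safety result for objective 1, which could come out too low in the subjects who received both treatments.

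**Working it through.** **Inputs.** Dose days D1, D22, D43, D64 and D85, and the D77 visit with its ±7-day window (flow chart, 6.0). Dosing window ±3 days (5.2.2 and 6.0). Recording ends 30 days after the last dose (7.1.2.1, 7.1.4.3, 8.1). Sample size 20 (section 1.0).

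**Schedule check.** Dose k falls on day 1 + 21(k − 1), which gives 1, 22, 43, 64, 85. This matches the flow chart.

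**Gap for a switched subject without maintenance.** Recording ends on day L + 30, where L is the last dose day. Gap = max(0, visit day − (L + 30)). The shortest gap uses a dose 3 days late and a visit on D70. The longest uses a dose 3 days early and a visit on D84.

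| Last dose | Recording ends | Gap to D77 | Shortest | Longest |
|---|---|---|---|---|
| Dose 2, D22 | 22 + 30 = D52 | 77 − 52 = 25 days | 70 − 55 = 15 | 84 − 49 = 35 |
| Dose 3, D43 | 43 + 30 = D73 | 77 − 73 = 4 days | 70 − 76 < 0, so 0 | 84 − 70 = 14 |
| Dose 4, D64 | 64 + 30 = D94 | none | none | 84 − 91 < 0, so 0 |

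Dose 2 is the central case because the day 35 marrow, taken after dose 2, is the first listed trigger for chemotherapy (5.2.1.2). A switch after dose 1 is discouraged but possible. It would end recording at 1 + 30 = D31, 77 − 31 = 46 days before D77. However, 5.7 says subjects with fewer than two doses may be replaced and remain monitored for study outcomes, so that case is less clear.

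**How much of the chemotherapy period is covered.** The documents give no chemotherapy start date. If it began on D36 (an assumption, the day after a nominal day 35 marrow), D36 to D77 is 42 days. Of these, D36 to D52 (17 days) are inside the window and D53 to D77 (25 days) are outside.

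**Effect on the rate.** Each subject whose only grade 3-5 regimen-related event falls in the gap lowers the reported incidence by 1/20 = 5 percentage points. Section 8.2.2 says only that several, but not all, patients are expected to receive chemotherapy, so the total cannot be computed.

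**SAE windows.** Taking the end of treatment as a last dose on D22, 7.2.3.1 gives 22 + 30 = D52 and 5.6 gives 22 + 90 = D112. The two differ by 60 days.

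**The case against.** The best defence is that the plan is consistent once its defined terms are used. The treatment period is defined in 7.1.4.3 and repeated in 8.1, and Table 2 lists only pembrolizumab as trial treatment. Read that way, cessation of treatment in 7.2 means the last pembrolizumab dose and agrees with 7.1.2.1. This stands. A reader might infer two adverse event windows of equal standing with nothing to choose between them, but the documents do not support that: pembrolizumab is the natural anchor. The footnote that puts "Subjects without CR / PR at day 77, relapse / progression after day 77 or clinically significant toxicity during the treatment" into the off-treatment group concerns maintenance eligibility and sets no recording window. Section 5.7 sets none either. The natural reading does not remove the problem, however, because the pembrolizumab-anchored rule is what produces the gap. The D77 adverse event review softens it only if new events found there are recorded, and 7.1.2.1 says they are not.

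Second, much is captured after D52. Total GvHD runs to 90 days after the last infusion (8.2.1). Events of clinical interest run to 90 days, or 30 if new anticancer therapy starts (7.2.3.2). Pembrolizumab-related SAEs are reportable at any time (7.2.3.1). Survival is followed. Subjects who start maintenance have a later last dose, so their treatment period spans the gap. All of this stands and narrows the loss mainly to new non-GvHD toxicity during chemotherapy.

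Third, a lost event changes incidence only if the subject has no other qualifying event, and part of the chemotherapy period lies inside the window. This also stands.

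A reader might also infer that the adverse event form cannot tell chemotherapy toxicity from leukemia complications. That is not shown. The form is not in the documents, progression is not an adverse event (7.2), and Table 6 asks the assessor to consider underlying disease and other drugs. What can be said is that the recorded relationship answer concerns the Merck product only.

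**Conclusion.** The point holds in a limited form. Under the plan's own rule, new adverse events in a subject switched after dose 2 without maintenance stop being recorded at about D52, 25 days (15 to 35) before the visit at which response is counted. The gap is 4 days (0 to 14) after dose 3 and nil after dose 4. RRT has no window of its own to override this, and the rule is at odds with the D77 review and with objective 1.

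The possible undercount is 5 percentage points per affected subject. Its total is unknown because the number switched, their chemotherapy dates and their event rates are not given. The result assumes that treatment means pembrolizumab, as 7.1.4.3 and Table 2 indicate.

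It would be wrong to conclude that safety monitoring is compromised more widely. The analysis is descriptive, and the toxicity stopping rule has its own window in 8.2.4 and is unaffected. The 90-day versus 30-day SAE statements contradict each other however treatment is read.

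**What to change.** For all subjects, record grade 3-5 non-hematologic adverse events to the later of 30 days after the last pembrolizumab dose and the D77 visit. Stop earlier only for death, withdrawal or the start of non-protocol therapy. Amend 7.1.2.1, 7.1.4.3, 7.2 and the flow-chart footnote to match. Recording has to be prospective, because on D53 the site cannot know who will start maintenance on D85.

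I would not tie the window to the last chemotherapy dose, since that would make observation times depend on the regimen chosen. Ending at D77 reduces the difference from a four-dose subject from 94 − 52 = 42 days to 94 − 77 = 17 days.

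In 8.2.1, define RRT over this window as grade 3-5 non-hematologic events related to pembrolizumab or protocol chemotherapy. Record the relationship to chemotherapy alongside the Table 6 item, and report RRT before and after the first chemotherapy dose. Use one SAE window in both 5.6 and 7.2.3.1, namely the 90 days that 5.6 states.

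The cost is a protocol amendment, one extra relationship item and a few more weeks of recording, mostly in switched subjects (nominally 25 days after dose 2, 4 after dose 3) and in anyone else who stops pembrolizumab early. More expected chemotherapy events will be recorded. The non-hematologic limit and the split at first chemotherapy keep the pembrolizumab-only period readable. The D77 review is already scheduled, at a single center with 20 subjects.
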